9.1 Primary Endpoint

9.1.1 Time to Liver Transplantation or Death Through 1 Year After Randomization

Time to one-year transplant-free survival will be calculated as the earlier of [(date of liver transplantation or date of death) – randomization date + 1] for those subjects who died or had a liver transplant within the analysis period. Subjects who neither died nor had a liver transplant within the analysis period will have their time to event censored at the earlier of the following times:

- Date of last contact.
- Cut-off date for analysis.

9.1.2 Primary Analysis

The analysis of the primary endpoint will be performed for the ITT population.

The objective of this study is to demonstrate superiority of SMT + Albutein 20% over SMT alone with regards to 1-year transplant-free survival. The null hypothesis is that the hazard functions for liver transplantation or death are the same for the 2 treatment groups, or equivalently, the hazard ratio is equal to 1. The alternative hypothesis is that the hazard functions for liver transplantation or death are not the same for the 2 treatment groups, or equivalently, the hazard ratio is not equal to 1.

Null Hypothesis H_0 : $HR(SMT + Albutein 20\% / SMT \text{ alone}) = 1$

Number	BIG-CL-SP-000319
Version	2.0
Status	Effective

IG1601 Statistical Analysis Plan

GRIFOLS

Bioscience Industrial Group

Alternate Hypothesis Ha: HR (SMT + Albutein 20% / SMT alone) $\neq 1$

The Hazard ratio and 95% CIs will be estimated using a stratified Cox Proportional-Hazards (PH) model, where the stratification factors include the region (Europe or North America) and history of hospitalization for acute decompensation of liver cirrhosis (yes or no) used in the randomization and recorded in IWRS.

Superiority will be demonstrated if the p-value of the estimate of the treatment effect from the PH model for SMT + Albutein 20% compared to the SMT alone group is less than or equal to 0.05 and the hazard ratio is less than 1.

The one -year transplantation-free survival will be summarized by means of Kaplan-Meier survival estimates and curves. The number and percentage of subjects with events of transplantation or death and subjects without events (censored) will be presented by treatment. The median, 25th percentile and 75th percentile for event-free survival in days will be calculated by treatment using Kaplan-Meier estimates, and the 95% confidence intervals (CI) for the median of each treatment group will be calculated using the Brookmeyer-Crowley method. The probability of event-free survival for the endpoint at day 31, 61, 91, 181 and 361 for the endpoint and 95% confidence interval (CI) will be estimated using the Kaplan-Meier product limit method and Greenwood's formula for standard error.

The survival functions will be compared between treatment groups using a log-rank test stratified by region (Europe or North America) and history of hospitalization for acute decompensation of liver cirrhosis (yes or no) as recorded in IWRS.

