6.1.3 Definition of Baseline

Baseline is defined as the last measurement taken prior to the start of study treatment for the SMT + Albutein 20% group and for the SMT alone group baseline is the last measurement taken on or prior to the Day 1 visit. For SMT + Albutein 20% subjects, two sets of vital signs assessments are collected on day of first infusion; the vital signs assessment time will be used to determine whether the vital signs were collected pre- or post-Albutein administration if assessment time is not available, then the vital signs designated by the investigator as pre-dose on the eCRF will be considered baseline. For all other assessments, if time of assessment is not available then an assessment that occurs on the same date as randomization is assumed to be prior to randomization and considered baseline.

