7.3 Demographics

Demographics (age, sex, race, ethnicity, country and region in Europe), baseline weight, and stratification factors for randomization will be listed and summarized. Subjects who were incorrectly stratified at the time of randomization will be listed and summarized.

Baseline characteristics listed above will be compared to evaluate possible imbalance by using Student's t test will be used for continuous variables, Chi-square test for binomial or nominal variables, and Poisson model for count variables (with adjustment for overdispersion). All demographic and baseline characteristics data will be listed. Summaries will be provided by treatment group for ITT.

In addition, the following baseline characteristics will be summarized; ACLF Grade, Ascites Grade, Ascites Refractory Occurrences, Ascites Refractory Type, CLIF-C ACLF Score, CLIF-C AD Score, CLIF-C OF Total Score, Child-Pugh Score, MELD Score.

GRIFOLS	IG1601 Statistical Analysis Plan			
	Number	BIG-CL-SP-000319	Version	2.0
	Status	Effective	Effective Date	09-Sep-2024
	Page			25 of 52

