9.1.3 Primary Efficacy Sensitivity Analyses

The primary analysis outlined in [Section 9.1.2](#) will be repeated using the per-protocol population as a sensitivity analysis.

..
An unstratified analysis will be performed as a sensitivity analysis on the ITT population.

In the event that clinically and statistically significant imbalances are observed between treatment groups in any of the subjects' baseline characteristics listed above in section 7.3, a sensitivity analyses will be performed in which treatment effects will be adjusted by those characteristics identified as having imbalances between treatment group by fitting an appropriate Cox PH model stratified by the region (Europe or North America) and history of hospitalization for acute decompensation of liver cirrhosis (yes or no) as recorded in IWRS. This will be performed on the ITT population.

A sensitivity analysis will be used to assess whether the magnitude of treatment effect (i.e., hazard ratio) is consistent between two CLIF-C AD subgroups (CLIF-C AD score >50 vs ≤ 50) by a stratified Cox model, where the stratification factors include the region (Europe or North America) and history of hospitalization for acute decompensation of

GRIFOLS	Number	IG1601	Version	2.0	Status	Effective	Effective Date	09-Sep-2024	Page	29 of 52
	IG1601 Statistical Analysis Plan									

liver cirrhosis (yes or no) as recorded in IWRS. CLIF-C AD category and treatment will be included as fixed effects and treatment by CLIF-C AD category interaction will also be included in the model. This will be performed on the ITT population.

The sensitivity analyses described above based on the ITT population will be repeated for the per-protocol population.

If the IWRS stratification factors region (Europe or North America) and history of hospitalization for acute decompensation of liver cirrhosis (yes or no) do not match with the corresponding information collected on the eCRF for more than 3% of subjects, the primary analysis will be repeated adjusting for the stratification variables as recorded on the eCRF. This will be performed on the ITT population only.

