9.1.4 Exploratory Subgroup Analyses (Primary Endpoint)

Subgroup analyses by age group (≤ 65 , > 65 years), sex, race (white, other), region (Europe, NA), history of hospitalization for acute decompensation of liver cirrhosis (yes, no), CLIF-C AD group (CLIF-C AD score > 50 , CLIF-C AD score ≤ 50), time to randomization from start of screening (≤ 3 days, > 3 days), ethnicity (Hispanic, non-Hispanic), country and European region (East Europe, West Europe, [see appendix 3](#) for details) will be carried out for the primary endpoint based on the ITT population.

In each defined subgroup category, the analysis will be carried out using the same methodology as outlined in [Section 9.1.2](#), and the hazard ratio and CI for the subgroup will be estimated. When the subgroup is defined by a stratification factor used for the randomization, the stratification factor will not be used in the stratified Cox PH model. For example, in the analysis of region or country subgroup, only the history of hospitalization for acute decompensation of liver cirrhosis (yes or no) will be used as the stratification factor in the stratified Cox PH model.

These results will be considered exploratory, due to both multiplicity concerns and small sample sizes that cannot be pre-specified. Only summary statistics and CIs will be presented; p-values will not be determined. A minimum of 30 subjects must be present in each subgroup category for the analysis to be performed.

The subgroup analysis based on the ITT population will be repeated for the per-protocol population.

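### The deciding Cox model is valid but leaves out baseline CLIF-C AD, which the SAP calls prognostic; adding the continuous score is a cheap improvement

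*SAP*

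**What the plan says.** SAP 9.1.2 estimates the hazard ratio in a Cox model stratified by the two randomization factors, with treatment as the only effect. The decision rule starts "Superiority will be demonstrated if the p-value of the estimate of the treatment effect from the PH model" and requires p of at most 0.05 with a hazard ratio below 1.

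SAP 12 describes CLIF-C AD as a prognostic score for this kind of patient and says the >50 entry criterion was brought in to raise the primary event rate. SAP 9.3.3 defines it as continuous, on a 0-100 scale. It is evaluated at screening (Protocol 7.2.1.1), where central-laboratory samples are also taken (SAP 5.2.1).

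For the primary endpoint the SAP uses the score in up to three ways:

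- **9.1.3, interaction model.** "CLIF-C AD category and treatment will be included as fixed effects and treatment by CLIF-C AD category interaction" enter a stratified Cox model, with the score cut at 50.
- **9.1.4, subgroups.** Hazard ratios are given on each side of 50. "Only summary statistics and CIs will be presented; p-values will not be determined".
- **9.1.3, imbalance-triggered model.** "In the event that clinically and statistically significant imbalances are observed between treatment groups", a Cox model adjusts for the unbalanced factors among the "baseline characteristics listed above in section 7.3, a sensitivity analyses will be performed".

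It is unclear whether the third reaches the score. SAP 7.3 says "Baseline characteristics listed above will be compared to evaluate possible imbalance", and only in a later paragraph that "the following baseline characteristics will be summarized; ACLF Grade, Ascites Grade, Ascites Refractory Occurrences, Ascites Refractory Type, CLIF-C ACLF Score, CLIF-C AD Score".

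**The concern.** The sponsor relied on the score's prognostic value to shape enrolment but does not use it in the deciding test. The interaction model addresses consistency of effect and does not give one overall hazard ratio. The subgroup estimates do not either. The triggered model depends on the data and may not cover the score. So no planned analysis gives an unconditional, pre-specified overall effect adjusted for continuous CLIF-C AD.

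Two things are at stake. If the score predicts outcome in the enrolled subjects, adjustment raises power with no extra subjects and no inflation of type I error. It also corrects for chance severity differences too small to trigger the imbalance analysis.

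**Working it through.** **Inputs from SAP 6.2 and 6.5.** 410 subjects, 1:1; 20% dropout; 1-year event rates 46% and 31%; two-sided alpha 0.05; 125 events for the log-rank version.

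**Reproducing the plan.**

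- Hazard ratio: ln(0.69)/ln(0.54) = 0.6022, as stated.
- Chi-square size per arm, pooled variance, no continuity correction: [1.960·√(2·0.385·0.615) + 0.842·√(0.46·0.54 + 0.31·0.69)]²/0.15² = 3.690/0.0225 ≈ 164. Then 164/0.8 = 205 per arm, or 410 in total, as stated.
- Log-rank power at 125 events (Schoenfeld): Φ(√125/2 · |ln 0.6022| − 1.960) = Φ(0.875) = 80.9%, consistent with the stated at least 80%.

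**Simulation.** 164 per arm followed for 1 year, so expected events are 164 × (0.46 + 0.31) = 126.3. Event times are exponential with a log-linear, standard-normal score. Hazards are calibrated so that the marginal rates stay at 46% and 31%. There are four equal strata with 1:1 allocation in each, stratified Cox Wald tests, and 20,000 runs per setting (simulation standard error about √(0.8·0.2/20,000) = 0.3 points). The hazard ratio (HR) per SD of the score is an assumption, because the documents give none.

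| Assumed HR per SD | Unadjusted power | Adjusted power | Gain (points) |
|---|---|---|---|
| 1.0 | 80.5% | 80.5% | 0.0 |
| 1.25 | 80.6% | 81.4% | 0.8 |
| 1.5 | 80.6% | 83.4% | 2.8 |
| 1.75 | 80.9% | 85.9% | 5.0 |
| 2.0 | 80.7% | 88.1% | 7.4 |

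In sample-size terms, 80.6% to 83.4% corresponds to [(1.960 + 0.970)/(1.960 + 0.863)]² = 1.077, about 8% more events or 32 more subjects on 410.

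**Effect of the >50 criterion.** The criterion narrows the score. SAP 12 says only that most patients enrolled under the final amendment, so the share of subjects affected was varied. The cut was placed at the population mean of a local score correlated 0.9 with the central one (both assumptions). Gains in points:

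| HR per untruncated SD | 50% of subjects | 70% | 100% |
|---|---|---|---|
| 1.25 | 0.5 | 0.6 | 0.3 |
| 1.5 | 2.0 | 2.1 | 1.3 |
| 2.0 | 6.1 | 5.4 | 3.8 |

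Moving the cut by 0.5 SD either way (70% share, HR 1.5) gives 2.1-2.2 points.

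**Type I error.** With 46% in both arms, six settings gave 4.8-5.1% adjusted and 4.7-5.0% unadjusted.

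**The imbalance trigger.** If it covers the score, a 5% t test fires in 4.8-5.3% of trials, and in fewer once clinical relevance is also required. About 12% of null trials show a non-significant imbalance favouring Albutein (p 0.05-0.30). Among these, false superiority at HR 1.5 is 5.3% unadjusted and 2.8% adjusted (nominal 2.5%, standard error about 0.4 points).

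**Missing scores and the estimate.** With 5% of scores mean-filled, adjusted power at HR 1.5 is 83.3%. The adjusted hazard ratio at HR 1.5 averages 0.588 against 0.600 unadjusted.

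**Cross-check.** A separately coded simulation without strata (4,000 runs per setting, no truncation) gave 82% to 84% at HR 1.5 and 82% to 89% at HR 2.0.

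**The case against.** **This is a preference, not a defect.** Protocol 9.1.2.1 compares the arms with a stratified log-rank test and keeps covariate-adjusted Cox models as sensitivity analyses. That is true: the planned test is valid, and the point is only that a better one is available at little cost.

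**The gain is small and rests on assumptions.** Prognostic strength, the position of the cut and the local-central correlation are all assumed. With the >50 criterion applied, the gain exceeds about 2 points only for a strongly prognostic score. This stands, and it limits the point to a modest improvement.

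**Removing 20% of subjects understates baseline power.** The ITT analysis keeps everyone and censors dropouts at last contact. With 205 per arm, 20% censored uniformly over the year (an assumption) and 70% of subjects under the criterion, there are about 143 events. Unadjusted power is then 85-86%, and the gain is about 0.5, 1.6 and 4.4 points at HR 1.25, 1.5 and 2.0. With complete vital status, events are about 158, unadjusted power is 88-89%, and the gain is 0.5, 1.5 and 4.0. The gain shrinks only slightly.

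**The false-superiority figure is selective.** It is. Trials with the opposite imbalance offset it, and overall type I error is about 5% either way. It describes protection within one trial, not a flaw in the test's error rate.

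**It may be too late.** The trial is open-label, SAP 2.0 is dated 09-Sep-2024, and lock status is not shown. If comparative data have been seen, the power gain is lost and only a supportive estimate remains.

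**The score is already in a 9.1.3 model, and Protocol 9.1.2.1 triggers adjustment on any baseline characteristic.** The first is dichotomized with an interaction and the second is conditional. Neither gives the missing estimate.

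**Conclusion.** The point holds as an improvement, not an error. The deciding model is valid and has its planned power under the design rates, but the plan never commits to one overall effect adjusted for continuous CLIF-C AD.

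For an assumed HR per SD of 1.25 to 2.0, adjustment adds about 0.8 to 7.4 points with an untruncated score, and 0.3 to 6.1 points across the truncation settings. If the score is uninformative, the gain is nil and no power is lost. Confidence in the size is medium: prognostic strength cannot be taken from the documents, and neither non-linear score effects nor non-proportional hazards were simulated.

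**What to change.** Before database lock and before any comparative look, amend the SAP as follows:

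- **9.1.2.** Add continuous CLIF-C AD to the stratified Cox model that decides superiority. Keep the unadjusted stratified Cox model and the stratified log-rank test as supporting analyses. Report both hazard ratios and label the adjusted one conditional.
- **Covariate definition.** Use the last central-laboratory value at or before randomization in both arms. The general rule in 6.1.3 differs by arm: "Baseline is defined as the last measurement taken prior to the start of study treatment for the SMT + Albutein 20% group", but on or before the Day 1 visit for SMT alone. If a sample from the day of randomization has no time, use the screening sample.
- **Missing scores.** Fill with the overall mean of both arms, so that every ITT subject stays in.
- **7.3.** State whether CLIF-C AD is among the characteristics tested for imbalance.
- **12.** List the change and state that no comparative data informed it.

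If comparative data have been seen, leave the deciding test as it is and add the adjusted model to 9.1.3 as supportive. Extending the adjustment to 9.2.1-9.2.5 is optional and was not quantified.

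The cost is one SAP amendment and one model term, with no new data or visits. There are three downsides. The hazard ratio becomes conditional while the planned 0.6022 is marginal. The covariate may differ from the baseline score summarized in 7.3 and used in 9.3.3. The deciding test also changes late in an open-label trial.

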9.1.3 Primary Efficacy Sensitivity Analyses

The primary analysis outlined in [Section 9.1.2](#) will be repeated using the per-protocol population as a sensitivity analysis.

..
An unstratified analysis will be performed as a sensitivity analysis on the ITT population.

In the event that clinically and statistically significant imbalances are observed between treatment groups in any of the subjects' baseline characteristics listed above in section 7.3, a sensitivity analyses will be performed in which treatment effects will be adjusted by those characteristics identified as having imbalances between treatment group by fitting an appropriate Cox PH model stratified by the region (Europe or North America) and history of hospitalization for acute decompensation of liver cirrhosis (yes or no) as recorded in IWRS. This will be performed on the ITT population.

A sensitivity analysis will be used to assess whether the magnitude of treatment effect (i.e., hazard ratio) is consistent between two CLIF-C AD subgroups (CLIF-C AD score >50 vs ≤ 50) by a stratified Cox model, where the stratification factors include the region (Europe or North America) and history of hospitalization for acute decompensation of

GRIFOLS	Number	IG1601	Version	2.0	Status	Effective	Effective Date	09-Sep-2024	Page	29 of 52
	IG1601 Statistical Analysis Plan									

liver cirrhosis (yes or no) as recorded in IWRS. CLIF-C AD category and treatment will be included as fixed effects and treatment by CLIF-C AD category interaction will also be included in the model. This will be performed on the ITT population.

The sensitivity analyses described above based on the ITT population will be repeated for the per-protocol population.

If the IWRS stratification factors region (Europe or North America) and history of hospitalization for acute decompensation of liver cirrhosis (yes or no) do not match with the corresponding information collected on the eCRF for more than 3% of subjects, the primary analysis will be repeated adjusting for the stratification variables as recorded on the eCRF. This will be performed on the ITT population only.

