5.1 Inclusion Criteria

Inclusion Criteria:

A subject must meet all the following inclusion criteria to be eligible for participation in this study:

- 1. Male or female subject ≥ 18 years of age.
- 2v5. Subjects with diagnosis of liver cirrhosis (based on clinical, laboratory, endoscopic, and ultrasonographic features or on histology).
- 3v5. Subjects who have been hospitalized for acute decompensation of liver cirrhosis with ascites (or with prior history of ascites requiring diuretic therapy) with or without ACLF at admission or during hospitalization but, without ACLF at Screening.
- 4v5. This criterion has been removed from Version 5 of the protocol.
- 5. In subjects with cirrhosis due to HBV, decompensation must occur in the setting of continuous (no less than 3 months) appropriate antiviral therapy.
- 6. In subjects with cirrhosis due to HCV, only decompensated patients who will not receive antiviral therapy during the study period will be included (subjects receiving antiviral therapy within 14 days prior to enrollment cannot be included in the study).
- 7. In subjects with cirrhosis due to autoimmune hepatitis, decompensation must occur in the setting of continuous immunosuppressive therapy.
- 8. Subjects must be willing and able to provide written informed consent or have an authorized representative able to provide written informed consent on behalf of the subject in accordance with local law and institutional policy.
- 9v5. CLIF-C score > 50 points at screening.

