10.4 Physical Assessment

Physical assessment findings (normal and abnormal) will be listed for each subject and summarized by treatment and visit. Any clinically significant abnormality, as determined by the investigator, experienced by a subject during the clinical study and not already present at baseline will be reported as an AE.

11 Interim Analysis

No interim analysis is planned.

12 Changes in Planned Analysis

During the conduct of the study, protocol amendments and varying recruitment rates between countries introduced potential variables to the study that will be analyzed for relevance to interpreting the outcomes on the efficacy endpoints. Specifically, the following variables will be analyzed as described further in the subsections below:

- Addition of CLIF-C AD > 50 as an inclusion criterion

GRIFOLS	Bioscience Industrial Group	Number	IG1601	IG1601 Statistical Analysis Plan
		Version	2.0	
Number	IG1601 Statistical Analysis Plan	Status	Effective	
		Effective Date	09-Sep-2024	44 of 52

Number	IG1601	IG1601 Statistical Analysis Plan
Version	2.0	
Status		
Effective		

Effective Date	09-Sep-2024
Page	45 of 52

- Number of subjects recruited per country and region in Europe (East and West Europe) as a subgroup analysis. Time from start of screening to randomization with first dose of IP as a subgroup analysis.
- Changes in the analysis of longitudinal outcomes.

Rationale and plan for subgroup analysis based on CLIF-C AD score

CLIF-C AD, a specific prognostic score for hospitalized cirrhotic patients with acute decompensation (18), was not an entry criterion in the study until Protocol Amendment 4, Version 5. In this amendment, the enrollment criteria that subjects needed a CLIF-C AD score >50 at screening was added to increase event rates for the primary efficacy endpoint. A subgroup analysis on the primary and secondary efficacy endpoints will be conducted comparing “CLIF-C AD score >50 ” vs “CLIF-C AD ≤ 50 ”. This subgroup analysis is incorporated into the appropriate sections above (See [Section 9.1.4](#)). This subgroup analysis is intended to address whether the study intervention demonstrates any differential effect on endpoints based on CLIF-C AD scores at enrollment.

Rationale and plan for subgroup analysis based on country recruitment

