Since this study is a large multinational study with varying rates of recruitment between countries, a subgroup analysis will be conducted for countries with reasonably large number of patients (30 patients). The objective of these analyses is to examine whether the patients in different countries benefit differently from the treatment possibly due to different standard medical treatment. This subgroup analysis is incorporated in the appropriate sections above (See [Section 9.1.4](#)). We do not conduct this subgroup analysis for countries with fewer patients because the model may not converge due to the fact that uncertainties in the parameter estimates become larger due to small sample size. For European countries an additional grouping based on the region in Europe the countries are located will be applied and subgroup analyses will be performed.

Rationale and plan for subgroup analysis based on time from start of screening to randomization with first treatment with IP

The time window from screening to first administration of Albutein 20% in the treatment arm has varied with protocol amendments. The final protocol amendment under which most of the patients were enrolled dictates that patients are randomized and receive first dose of IP within 3 days (72 hours) of start of screening, whereas earlier versions allow for the first dose of IP to occur more than 3 days (72 hours) after start of screening. To account for any possible differential treatment effect based on time to treatment with IP, a subgroup analysis will be done comparing subjects with time to randomization from start of screening ≤ 3 days vs time to randomization from start of screening >3 days. This subgroup analysis is incorporated in the appropriate sections above (See [Section 9.1.4](#)).

Discussion of the definition of TEAE in the SAP

In the protocol, a TEAE is defined as an AE which occurs between the start of study treatment and the final visit of the clinical study. In this SAP, TEAEs are defined as AE

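### The planned CLIF-C AD interaction cannot separate score from enrolment era, because scores of 50 or below come almost only from before Version 5; a restricted or version-adjusted supplement would help

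*SAP*

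**What the plan says.** SAP 9.1.3 plans this analysis among the primary-endpoint sensitivity analyses: "A sensitivity analysis will be used to assess whether the magnitude of treatment effect (i.e., hazard ratio) is consistent between two CLIF-C AD subgroups". The model is a Cox model stratified by region and prior hospitalization for acute decompensation. Its terms are given as "CLIF-C AD category and treatment will be included as fixed effects and treatment by CLIF-C AD category interaction". SAP 9.1.4 repeats the >50 versus ≤50 split as an exploratory subgroup.

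SAP Section 12 gives the history. CLIF-C AD "was not an entry criterion in the study until Protocol Amendment 4, Version 5". The rule that "subjects needed a CLIF-C AD score >50 at screening was added to increase event rates for the primary efficacy endpoint" came with that amendment, and it remains in the current protocol (Version 6, Section 5.1: "9v5. CLIF-C score > 50 points at screening"; the synopsis names the score as CLIF-C AD). Section 12 also refers to "The final protocol amendment under which most of the patients were enrolled" and says: "The time window from screening to first administration of Albutein 20% in the treatment arm has varied with protocol amendments".

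The purpose is stated in terms of the score: "This subgroup analysis is intended to address whether the study intervention demonstrates any differential effect on endpoints based on CLIF-C AD scores at enrollment".

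**The concern.** Once the >50 rule applied, nobody eligible could have a score of 50 or below. The comparison of high with low scores is therefore also, to a large extent, a comparison of late with early enrolment. Other features moved between versions too: Protocol 5.1 and 5.2 mark many criteria as modified in or removed from Version 5.

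The 9.1.3 model has no term for protocol version or enrolment period, and 9.1.4 does not list protocol version as a subgroup. If the treatment effect differed between eras for some reason other than the score, the interaction would pick that up and Section 12 would have it read as effect modification by severity. At stake is the interpretation of one prespecified sensitivity analysis, and through it any statement about which patients benefit more. The primary conclusion is not at stake.

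**Working it through.** **1. The plan's own figures.** SAP 6.2 assumes 1-year event rates of 46% and 31%. The hazard ratio is ln(0.69)/ln(0.54) = 0.602 and the control hazard is −ln(0.54)/365 = 0.0017 per day, as stated. With 125 events, power is Φ(√125/2 × |ln 0.6022| − 1.96) = 80.9%, in line with the stated 80%. These figures hold. The SAP gives none for the CLIF-C AD comparison.

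**2. How far score and era overlap.** Let f be the share of all subjects enrolled under Version 5 or later, and q the share of earlier subjects with a score >50. The SAP says only that most enrolled under the final amendment, so f > 0.5 (the >50 rule applied whether that means Version 5 or 6). It does not give q; 0.3 to 0.7 is assumed.

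Late share of the >50 group: w = f / [f + (1 − f)q]. Number with ≤50: 410 × (1 − f)(1 − q).

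| f | w for q = 0.7 to 0.3 | subjects ≤50 for q = 0.7 to 0.3 |
|---|---|---|
| 0.6 | 68% to 83% | 49 to 115 |
| 0.7 | 77% to 89% | 37 to 86 |
| 0.8 | 85% to 93% | 25 to 57 |

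Since q cannot exceed 1, w is never below f. The direction of the imbalance follows from the text; its size is an assumption. In the ≤50 group the late share is close to zero. Exceptions are eligibility deviations and subjects whose local screening value (SAP 5.2.1) exceeds 50 but whose central-laboratory value (the source for derived scores in SAP 9.3) does not.

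**3. What an era difference would do.** Suppose the score has no influence on the treatment effect. Approximately, ln HR(>50) = (1 − w) ln HR(early) + w ln HR(late), and HR(≤50) = HR(early). The apparent interaction ratio is HR(>50)/HR(≤50).

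| assumed HR early / late | w = 0.6 | w = 0.8 | w = 0.9 |
|---|---|---|---|
| 0.80 / 0.55 | 0.80 | 0.74 | 0.71 |
| 0.75 / 0.60 | 0.88 | 0.84 | 0.82 |
| equal in both eras | 1 | 1 | 1 |

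The last row matters: a shift in baseline risk alone does not create an interaction.

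**4. Whether adjustment can separate the two.** A small simulation used 410 subjects, 300 runs, q = 0.5, 20% dropout, and event rates of 46% (>50) and an assumed 30% (≤50). It took an extreme case: HR 1.0 early, 0.6022 late and no score effect. The planned model gave ratios of about 0.69 (f = 0.6) and 0.67 (f = 0.7). Adding version and treatment-by-version gave about 1.00 and 0.97. With equal effects in both eras the planned model gave about 1.11 and 1.05, near 1 for so few runs and events.

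**5. Precision.** Assume an event rate of 38.5% in >50 (the mean of 46% and 31%) and 25% to 35% in ≤50. Take 10% of events as lost, about half of the 20% dropout. Over f = 0.6 to 0.8 and q = 0.3 to 0.7 the ≤50 group has about 6 to 36 events. The standard error of the log interaction ratio is √(4/d₁ + 4/d₂), with d₁ and d₂ the events in each group:

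- Planned model, best case: √(4/36.2 + 4/102.3) = 0.39; worst case: √(4/5.5 + 4/133.5) = 0.87. The 95% limits span a factor of 2.1 to 5.5 each way.
- Pre-Version 5 only, best case: √(4/25.8 + 4/28.4) = 0.54; worst case: √(4/5.5 + 4/19.9) = 0.96. The factor is 2.9 to 6.6.

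The largest distortion in step 3 is |ln 0.71| = 0.34, below the smallest standard error. Under step 3's hazard ratios, a 5% interaction test would reject about 6% to 13% of the time over this grid.

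**The case against.** A reader might infer that the trial would wrongly conclude that benefit depends on CLIF-C AD. The documents do not support that. Distortion requires the treatment effect itself to differ by era, and nothing in either document says it does; the era hazard ratios above are invented for illustration. Even if they were true, the comparison is too imprecise to mislead often.

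A reader might also infer that the subgroup hazard ratios are biased. They are not: treatment is randomized, so each is a fair comparison for its own patients. Only attributing the difference to the score is in doubt.

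Nor does any decision depend on the analysis. Superiority rests on the overall ITT model (SAP 9.1.2), the fixed sequence (6.5) does not include the interaction, 9.1.3 sets no threshold for it, and 9.1.4 calls subgroup results exploratory and reports no p-values.

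The SAP is not silent on amendments. Section 12 says openly that they introduced variables to examine, and 9.1.4 has a ≤3 versus >3 days subgroup that Section 12 ties to protocol version. That subgroup is run separately, however, and does not adjust the 9.1.3 model.

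Some era differences that come to mind are not documented. Section 12 does not say which amendment changed the dosing window. Neither document says that earlier versions differed on starting in hospital or after discharge, or that standard care changed over time. The COVID-19 exclusion arrived with Version 6, so it does not mark the Version 5 boundary.

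All of this stands, and it limits the point to interpretation. It does not remove the structural overlap or the missing version term.

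**Conclusion.** The point holds in a limited form. By design the ≤50 group is essentially all pre-Version 5 and the >50 group mostly late, so the 9.1.3 interaction cannot distinguish score from era if the treatment effect varies by era. Whether it varies is unknown, and no enrolment count by version is given. Under the assumed era effects the apparent ratio would be about 0.71 to 0.88, within roughly one standard error. The primary test and the separate subgroup estimates are unaffected. This is an inexpensive improvement to a prespecified sensitivity analysis, not a threat to the trial's conclusion.

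**What to change.** Keep the planned 9.1.3 model and add two supplementary analyses.

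- (a) Fit the same treatment-by-CLIF-C AD interaction in subjects enrolled before Version 5, where both categories exist by design. The alternative is the all-subject model with protocol version and treatment-by-version added, which draws its score contrast from almost the same subjects.
- (b) Add protocol version (before Version 5 versus Version 5 or later) as a descriptive subgroup in 9.1.4.

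State in Section 12 that a difference will be attributed to CLIF-C AD score only if (a) is consistent with it.

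The cost is SAP wording and a few model runs on data already held, provided the version each subject enrolled under is on file. The loss is precision: (a) rests on few ≤50 events, so it should be reported as an estimate with its confidence interval and not as a test.
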